#### 4.6. Study Activities (Unscheduled and Post-Treatment Visits)

Tests and Assessments	End of Study Visit 	Unscheduled Relapse Assessment Visit 	Premature Study Treatment Withdrawal Visit 	Lymphocyte Follow-Up (Up to 96 Weeks After Last Dose) 
Physical Examination		X	X	
Vital Signs	X	X	X	X
Hematology	X 	X	X 	X
Blood Chemistry	X	X	X	
Urine Pregnancy Test 	X	X	X	
Urinalysis	X 	X 	X 	
Brain MRI  Scan ± Gd 	Scheduled MRI scans were performed in protocol versions 1 through 6.			
EDSS		X	X	
Visual Function Test		X	X	
SF-36 and EQ-5D		X	X	
Relapse Assessment		X		
Concomitant Therapy and Procedures Recording	Monitor and record throughout the study as per Section 11.6			
AE/SAE Reporting	Monitor and record throughout the study as per Section 15			

AE = adverse event; EDSS = Expanded Disability Status Scale; EQ-5D = EuroQol EQ-5D Health Survey; Gd = gadolinium; LLN = lower limit of normal; MRI = magnetic resonance imaging; SAE = serious adverse event; SF-36 = Short-form 36 Health Survey.

1. For subjects who have already completed Visit 36 or beyond, an End of Study Visit should be completed 4 weeks after their next visit (scheduled or unscheduled).
2. Unscheduled Relapse Assessment Visit is to be carried out within 5 days of suspected relapse.
3. Subjects who permanently discontinue BG00012 prior to Week 384 (Visit 36) should complete a Premature Study Treatment Withdrawal Visit within 4 weeks of their last dose. The Premature Study Treatment Withdrawal Visit will serve as the End of Study Visit..
4. Lymphocyte follow-up as per Section 11.3.
5. For women of childbearing potential.
6. If urinalysis is abnormal, see Section 11.2.
7. Only in subjects who had MRI scans as part of Studies 109MS301 and 109MS302 and in 109MS303 up through and including Amendment 6.
8. MRI must not be performed within 30 days of receiving a course of steroid.

CONFIDENTIAL

The information contained herein may not be used, disclosed, or published without the written consent of Biogen MA Inc.

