**Table 3: Lymphocyte Monitoring and Management for Subjects Who Have a Lymphocyte Count  $<500/\text{mm}^3$**

For subjects who have a lymphocyte count  $<500/\text{mm}^3$ , the Investigator should repeat the test as soon as possible. If re-test confirms that the lymphocyte count remains  $<500/\text{mm}^3$ , lymphocyte counts should be monitored every 4 weeks while on BG00012.

If subject has lymphocyte counts  $<500/\text{mm}^3$  for  $\geq 24$  weeks, subject meets the **Temporary Withholding Rule** and BG00012 will be temporarily withheld. If the Temporary Withholding Rule is not met, the subject will be monitored every 12 weeks.

CONFIDENTIAL

The information contained herein may not be used, disclosed, or published without the written consent of Biogen MA Inc.

Lymphocyte Monitoring for Subjects Meeting the Temporary Withholding Rule	Management for Subjects Meeting the Temporary Withholding Rule

The subject will be monitored every 4 weeks for 24 weeks, then every 12 weeks until the lymphocyte count is <math>\geq</math>LLN OR for 96 weeks after their last dose, whichever is earlier. However, if a subject reaches the end of study and their lymphocyte count remains <math><</math>LLN, the subject will be monitored every 12 weeks until the lymphocyte count is <math>\geq</math>LLN OR for 48 weeks after their last dose, whichever is earlier.
	
 
• If lymphocyte count remains <math><500/\text{mm}^3</math> for 24 weeks after temporary withdrawal, BG00012 must be permanently discontinued.
 
• If lymphocyte count is between <math>\geq 500/\text{mm}^3</math> and <math>\leq 800/\text{mm}^3</math>, then BG00012 will continue to be temporarily withheld.
 
• If lymphocyte count recovers to <math>>800/\text{mm}^3</math> (confirmed by 2 tests, at least 4 weeks apart), the physician/patient has the option to restart BG00012. If, upon resumption of BG00012, the lymphocyte count is <math><500/\text{mm}^3</math> on 1 occasion (confirmed by repeat testing), then BG00012 must be permanently discontinued.
 
• Alternative disease-modifying treatmenta may be considered, at the discretion of the treating physician as per standard of care. Subjects treated with alternative disease-modifying treatment will not have the option to restart BG00012.
 

AE = adverse event; CRF = case report form; LLN = lower limit of normal.

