### **15.2. Monitoring and Recording Events**

#### **15.2.1. Adverse Events**

Any AE experienced by the subject from the time of first dose of BG00012 until the final study visit (including, but not limited to, the lymphocyte follow-up visits [for applicable subjects]) is to be recorded on the CRF, regardless of the severity of the event or its relationship to BG00012.

CONFIDENTIAL

The information contained herein may not be used, disclosed, or published without the written consent of  
Biogen MA Inc.

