#### Clinical Adverse Events

Only treatment-emergent AEs will be presented in the summary tables. Treatment-emergent is defined as having onset date which is on or after start of study treatment, or that is worsened after the start of study treatment.

The incidence of treatment-emergent AEs will be summarized by treatment group, overall, by severity, and by relationship to study treatment. The summary tables will include incidence estimates for overall system organ class as well as for preferred terms within each system organ class.

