6.5.3 Analysis of Adverse Events

All summary analyses of AEs will be based on the principle of treatment emergence. In a given dataset, an event is considered to be treatment emergent if it has an onset date on or after the date of first study treatment or if it was present prior to start of study treatment and subsequently worsened. Henceforth, whenever an analysis or summary of AEs is mentioned, it is intended that this is in reference to the treatment emergent adverse event experience, even if not explicitly mentioned.

In general, analyses of AEs will include all events through the end of a subject's follow-up in a given dataset.

In general, AEs will be analyzed based on *incidence*, defined as the proportion of subjects who had at least one occurrence of an event out of the number of subjects in the relevant safety analysis population.

The Medical Dictionary for Regulatory Activities (MedDRA) version 13.1 will be utilized to code and group AEs by System Organ Class (SOC) and Preferred Term (PT). References to summaries of AEs using System Organ Class are intended to refer to the primary SOC. In addition to summaries of incidence by both SOC and PT, incidence of adverse events may also be summarized and presented by SOC only or by PT only, as appropriate, depending on the nature of the analysis performed. Adverse event summaries may also be provided by

High-Level Group Term (HLGT) or High-Level Term (HLT), if considered appropriate for signal detection, in instances where the SOC level of summary is too broad but the PT level of summary is too granular.

A summary analysis of adverse events will be provided including the following numbers and incidences/percentages of subjects: in the safety analysis population; with an adverse event; with a moderate or severe AE; with a severe AE; with a related AE; with a serious adverse event (SAE); with an AE leading to discontinuation of study treatment; and with an AE leading to withdrawal from study.

Summaries of the most frequently reported AEs by PT will also be presented, defined as those AEs with an incidence of AEs of at least 5% (at SOC or PT level) in any treatment group. Other cutoff values may be explored, as appropriate.

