- Gastrointestinal tolerability;
- Infections, including potential opportunistic infections;
- Ischaemic cardiovascular disorders;
- Hepatic disorders;
- Renal disorders;
- Malignancies;
- Lymphopenia and Leukopenia.

Subjects who discontinue study treatment are to have a premature study withdrawal visit within four weeks of the last dose of study treatment dose and a telephone follow-up 12 weeks after the last dose of study treatment. For subjects who have discontinued study treatment, a separate summary of adverse events with onset after discontinuation of study treatment may be presented.

Subject narratives will be provided for the following event types in Study 109MS303:

- Deaths:
- Serious adverse events (only selected SAEs may be included);
- AEs leading to study drug discontinuation;
- AEs leading to study withdrawal;
- Special interest AE categories of potential opportunistic infections, ischaemic cardiovascular disorders, hepatic disorders, and malignancies;
- ALT or AST values >5xULN at any time post-baseline; and
- ALT or AST values $\ge 3xULN$ and concurrently total bilirubin values $\ge 2xULN$.

Select AE analyses utilizing the Study 109MS303 Safety Population with Study 109MS303 Treatment Grouping and Study 109MS303 data only, mentioned in the second bullet in Section 6.5.1 above, may include, but are not limited to: summary analysis of adverse events (AEs), incidence of AEs by SOC and PT, incidence of most common AEs, incidence of treatment-related AEs, incidence of severe AEs, incidence of serious adverse events (SAEs), incidence of treatment-related SAEs, incidence of AEs that led to discontinuation of study drug, incidence of AEs that led to study withdrawal, and incidence of AEs of special interest such as malignancies, hepatic disorders, GI, opportunistic infections, herpes zoster, etc.

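### AE counting has no end bound, so the main safety tables mix on-drug, off-drug and post-switch events over unequal follow-up; required on-treatment tables should be added

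*SAP*

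**What the plan says.** **Start of counting.** In SAP 6.5.3, "an event is considered to be treatment emergent if it has an onset date on or after the date of first study treatment", or if an existing condition worsens later. Protocol 16.4.2 agrees: "Treatment-emergent is defined as having onset date which is on or after start of study treatment". Neither gives an end date.

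**End of counting.** SAP 6.5.3 states, as a general rule, that "analyses of AEs will include all events through the end of a subject's follow-up in a given dataset". The measure is the proportion of the safety population with at least one event. SAP 6.2.1 keeps subjects in their randomized or assigned group, and every such group is a BG00012 group.

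**Collection.** Protocol 15.2.1 says that any AE from the first dose "until the final study visit (including, but not limited to, the lymphocyte follow-up visits [for applicable subjects]) is to be recorded on the CRF".

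**Length of off-drug follow-up in the current protocol.**
- Early stoppers with a normal lymphocyte count: a withdrawal visit no later than 4 weeks after the last dose, which doubles as the End of Study Visit (Protocol 4.6).
- Others who complete or stop with a count below LLN: up to 48 weeks (Protocol 11.3).
- Subjects meeting the Temporary Withholding Rule: up to 96 weeks, or 48 if they reach the end of the study still below LLN (Protocol Table 3).
- In both lymphocyte groups, follow-up ends earlier on recovery.

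**Switching.** Protocol Table 3 allows another disease-modifying drug for subjects under the Temporary Withholding Rule: "Subjects treated with alternative disease-modifying treatment will not have the option to restart BG00012". Its footnote requires AEs of such therapy to be documented. The note in Protocol 11.4 keeps subjects below LLN in the study whatever listed reason made them stop, and receiving a disallowed medication is one of those reasons.

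**The one separate view.** SAP 6.5.3 says that for subjects who stopped treatment "a separate summary of adverse events with onset after discontinuation of study treatment may be presented".

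**The concern.** Long-term safety is the primary objective, and the AE tables are its main output. A table headed by a BG00012 dose group is naturally read as experience on that drug. Under the stated rule it also contains events that began months after the last dose, and some that began on another disease-modifying drug. Because the measure is a crude proportion, off-drug time can add subjects with events while the denominator stays the same.

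The added time is also uneven: lymphocyte status at stopping determines how long a subject is watched. Infections, opportunistic infections and malignancies are special-interest categories in SAP 6.5.3, and for rare events a few post-switch cases could change how a row is read. The optional post-discontinuation summary takes nothing out of the main tables.

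**Working it through.** The plan has no sample size, power or event-rate figure to reproduce (Protocol 16.7 and SAP 5 state there is no formal calculation). The check is a reading of the rules side by side, then a scale calculation under assumptions.

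**1. End bounds within the SAP**

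| Data | End bound | SAP section |
|---|---|---|
| Exposure | last dose | 6.3.6 |
| Concomitant medication | last dose (a 180-day extension may apply to some completers) | 6.3.7 |
| Efficacy, in general | first alternative MS medication | 6.4.2 |
| AEs | end of follow-up | 6.5.3 |

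The AE numerator therefore covers time that the exposure figure does not, and safety has no counterpart to the efficacy cut.

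**2. Follow-up windows**

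Against a 4-week visit, the caps give 48/4 = 12 and 96/4 = 24. Against the 12-week telephone call still cited in SAP 6.5.3, they give 48/12 = 4 and 96/12 = 8. The amendment history shows earlier versions with that call for all subjects and, once introduced, at most 24 weeks of lymphocyte follow-up: 24/12 = 2. All of these are ratios of maxima.

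**3. Off-drug subject-years, upper bounds**

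Years = weeks × 7/365.25, so 4, 48 and 96 weeks are 0.0767, 0.9199 and 1.8398 years. N = 1738 (SAP 2.1). The amendment rationale on prolonged lymphopenia gives 2% of subjects with counts below 0.5 × 10⁹/L for at least six months; this is used as a proxy for the Temporary Withholding Rule.
- 0.02 × 1738 = 34.76, about 35 subjects; 35 × 1.8398 = 64 subject-years.
- Assumed share s of other subjects stopping below LLN, 10% to 40%: 0.10 × 1738 × 0.9199 = 160, and 0.40 × 1738 × 0.9199 = 640 subject-years.

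**4. Chance of at least one off-drug event**

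P = 1 − exp(−λt), with an assumed constant rate λ per subject-year.

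| λ | 4 weeks | 48 weeks | 96 weeks |
|---|---|---|---|
| 0.01 | 0.08% | 0.92% | 1.82% |
| 0.05 | 0.38% | 4.50% | 8.79% |
| 0.20 | 1.52% | 16.81% | 30.79% |

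**5. Effect on whole-group crude incidence**

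Let T be on-drug time (assumed 2, 5 or 8 years) and p(w) = 1 − exp(−λ(T + w × 7/365.25)). The 4-week cut gives p(4). All follow-up gives (1 − s − 0.02)p(4) + s·p(48) + 0.02·p(96).
- Largest rise (T = 2, λ = 0.20, s = 0.40): p(4) = 33.99%, p(48) = 44.23%, p(96) = 53.60%. Then 0.58 × 33.99 + 0.40 × 44.23 + 0.02 × 53.60 = 38.48%, a rise of 4.49 points.
- Smallest rise (T = 8, λ = 0.01, s = 0.10): 7.76% becomes 7.87%, a rise of 0.11 points.
- Rare events (λ = 0.01) across all T and s: a rise of 0.11 to 0.36 points, or 0.0011 × 1738 ≈ 2 to 0.0036 × 1738 ≈ 6 more subjects with an event.

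For one subject followed the full 96 weeks, p(96)/p(4) runs from 86.03/80.12 = 1.07 (T = 8, λ = 0.20) to 3.77/2.06 = 1.83 (T = 2, λ = 0.01).

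**The case against.** The case on the other side is substantial.

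- **Follow-up is shorter than the caps suggest.** It stops at recovery, and 96 weeks applies only under the Temporary Withholding Rule. Many subjects also left under older rules. The amendment extending the study to 12 years mentions about 1000 ongoing patients against 1738 randomized, so roughly 700 had gone by then. This stands, and it rules out a 12- to 24-fold contrast as a description of the data.
- **Treatment-emergent is a timing label.** SAP 6.5.3 tabulates investigator-assessed relationship separately, lists each SAE with onset date and relationship, and plans narratives for deaths, opportunistic infections and malignancies. This stands: a reader might infer that post-switch events are causally attributed to BG00012, and the SAP does not do that. Narratives and listings do not, however, correct the SOC/PT or special-interest rows.
- **Late counting can be right.** The rationale for the longer lymphocyte follow-up says recovery may take more than 6 months after stopping. Events in that time may reflect the drug, so counting them is a defensible conservative choice, and it matches the protocol's definition. This stands and argues against replacing the main tables with a 4-week cut.
- **Interval tables show the number followed.** They are optional, and their denominators do not separate on-drug from off-drug time. This answers little.

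**Conclusion.** The point holds in a limited form. The rule has no end bound, off-drug AE recording lasts longer for subjects below LLN, some may be on another disease-modifying drug, and the only separate view is optional. The main tables will therefore mix three kinds of time that a reader cannot pull apart.

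The whole-group effect is probably modest: about 0.1 to 4.5 percentage points. That range rests on assumed rates of 0.01 to 0.20 per subject-year (equal on and off drug), assumed shares of 10% to 40% stopping below LLN, assumed on-drug time of 2 to 8 years, and follow-up to the cap for everyone below LLN. The mixing matters most for rare special-interest events, where a handful of cases can change the reading.

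A reader might go further and infer that the plan will manufacture a link between lymphopenia and infection. The documents do not support that: no visible text plans AE incidence by lymphocyte status, and parts of the SAP are redacted. The unequal follow-up would become a bias only if such a comparison were made.

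**What to change.** 1. Keep the all-follow-up tables as specified.
2. Add required on-treatment tables for AEs, SAEs and special-interest AEs. Count from first dose to last dose plus a prespecified window (for example the 4-week withdrawal-visit window), or to the start of alternative MS medication if earlier.
3. Report these with the subject-years already computed under SAP 6.3.6. Exposure there ends at last dose, so either add the window or footnote the difference. The overall time on study in the same section suits the all-follow-up tables.
4. Make the post-discontinuation AE summary in SAP 6.5.3 required, and split it into events before and after the start of alternative MS medication.
5. Reconcile the follow-up lengths that define the end of counting: up to 96 weeks in Protocol Table 3 and in the SAP 3.6 schedule, 48 weeks in SAP 6.5.6, and the 12-week call in SAP 6.5.3, which is absent from the current schedule in Protocol 4.6.

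The cost is a few SAP sentences and one extra set of tables from data already collected. The protocol's definition of treatment emergence is untouched. Late-onset events are absent from the on-treatment tables but stay visible in the all-follow-up ones. Off-drug gaps during temporary withholding still count as on-treatment when dosing resumes; a footnote should say so.

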6.3 Description of Analytic Methods

6.3.1 Analysis of Baseline Data

Baseline data will be summarized utilizing the Study 109MS303 ITT Population and both Combined Treatment Grouping and Study 109MS303 Treatment Grouping. The definition of baseline will be dependent on the analysis performed and the study data utilized.

The following are the various definitions of baseline that may be utilized in analyses:

- Study 109MS303 Baseline is defined as the latest available value prior to or on the date of first dose of study treatment in Study 109MS303;
- Previous Study Baseline is defined as the latest available value prior to or on the date of first dose of study treatment in Study 109MS301 or 109MS302; and
- BG00012 Treatment Baseline is defined as the latest available value prior to or on the date of first exposure to BG00012, specifically:

- the latest available value prior to or on the date of first exposure to study treatment in Study 109MS301 or 109MS302 for subjects on BG00012 treatment in Study 109MS301 or 109MS302;
- o the latest available value prior to dosing in Study 109MS303 for subjects in the placebo or GA treatment groups in Study 109MS301 or 109MS302.

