6.3.6 Study Drug Compliance and Time on Study

Study drug compliance in Study 109MS303 will be summarized. The number of capsules not taken since the previous visit (out of those capsules the subject was expected to take) is collected on the study drug accountability CRF page. Using this information, percentage compliance will also be calculated as follows:

Total number of capsules not taken is calculated as the sum of all individual values of the number of capsules not taken since the previous visit for a subject, as defined above.

Total number of capsules assigned is calculated based on the number of days on study medication for a subject. The calculation of number of days on study medication is detailed below.

Percentage compliance is then calculated as: [(Total number of capsules assigned) – (Total number of capsules not taken)] / (Total number of capsules assigned) * 100.

Percentage compliance will be calculated up to the date of last dose in Study 109MS303.

In addition, the total time on study medication will be summarized as a continuous variable and categorized into intervals. Days on study medication is calculated as the number of days from date of first dose to date of last dose. Additionally, the total number of subject-years of exposure to study medication will be presented. Time on study medication will be summarized for Study 109MS303 only and for Combined Data, utilizing the Study 109MS303 ITT and Safety populations.

Time on study parameters, including overall time on study and time on study prior to first use of alternative MS medication, will be summarized as a continuous variable and categorized into intervals. Total number of subject-years for time on study, both overall and prior to first use of alternative MS medication, will also be presented with respect to the dataset analyzed. The last known date on study will be taken as the last visit/evaluation date from relevant data for a subject. Summaries will be performed for Study 109MS303 only and for Combined Data, utilizing the Study 109MS303 ITT population. Additionally, overall time on study in Study 109MS303 will be summarized utilizing the Study 109MS303 Safety population.

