Annualized relapse rate (ARR) will be summarized using the following analysis populations, treatment grouping, and datasets:

- Studies 109MS301/302/303 ARR, overall and over time, using the Study 303 ITT Population with Combined Treatment Grouping and Combined Data; and
- Study 109MS303 ARR using the Study 303 ITT Population with Combined Treatment Grouping and Study 109MS303 data only.

The number of subjects with a given number of relapses (categories of 0, 1, 2, 3, and 4 or more relapses), total number of relapses, and total number of subject-years of follow-up will be summarized by treatment group. The unadjusted ARR will be calculated for each treatment group as the total number of relapses divided by the total number of subject-years

of follow-up. Relapses and follow-up time that occur after first use of alternative MS medications are excluded from the calculations.

The adjusted ARR and associated 95% confidence interval will be calculated for each treatment group by using a negative binomial regression model for unadjusted ARR, adjusting for baseline EDSS score (≤2.0 vs. >2.0), baseline age (<40 vs. ≥40 years old), region, and baseline relapse rate (i.e., the number of relapses in the year prior to the date of first dose in the previous study) as covariates. The baseline definition for these covariates will be based on Previous Study Baseline.

The logarithmic transformation of the time on the study will be included in the model as the "offset" parameter. If the data are underdispersed, or if the negative binomial regression model does not converge, a Poisson regression model with the same covariates will be used instead of the negative binomial regression model. Dispersion will be evaluated from the Pearson Chi-Square statistic. If the ratio of the Pearson Chi-Square statistic to the degrees of freedom is ≤ 1 which indicates no overdispersion, then a Poisson regression model with adjustment for underdispersion will be used.

In addition, the subject relapse rate will be calculated as the number of relapses for an individual subject divided by follow-up time in years for that subject excluding follow-up time after first use of alternative MS medication. Subject relapse rate will be summarized descriptively by treatment group.

ARR analyses over time will be presented by various time intervals in order to elucidate onset and maintenance of effect over time. For example, time intervals one year in length may be considered.

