6.5 Safety Data

6.5.1 Analysis Population

Analysis populations, treatment groupings, and datasets are detailed in Section 6.2 above.

Study 109MS303 Safety Population is defined to include all subjects who received at least one dose of study treatment in Study 109MS303 and had any post-baseline safety follow-up in Study 109MS303, defined as any treatment emergent AE in Study 109MS303 or any post-baseline laboratory, vital signs, or physical exam assessment in Study 109MS303. This definition of the safety population is utilized in order not to inflate the denominator for calculation of incidences and percentages (and therefore deflate the incidences and percentages themselves) with subjects who were dosed in Study 109MS303 but had no post-baseline safety follow-up.

The analysis populations, treatment groupings, and datasets for safety analyses will be as follows:

- Primary safety analyses will utilize the Study 109MS303 Safety Population with Combined Treatment Grouping and Study 109MS303 data only; and
- Select safety analyses (where the incidence in Study 109MS303 itself may be of interest) will utilize the Study 109MS303 Safety Population with Study 109MS303 Treatment Grouping and Study 109MS303 data only.

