The incidence of AEs by SOC and PT may also be presented by time intervals (e.g., using a 12 month time interval). Other time intervals may be explored as well to elucidate trends over time. For such analyses, for a given time interval, the number of subjects who were followed for adverse events during that time interval will be presented along with the AE incidence during that time interval. Therefore, for a given SOC or PT, subjects will be counted only once for a given time interval but may be counted more than once across time intervals.

The incidence of AEs by relationship to study treatment will be summarized by SOC and PT. For a given SOC or PT, subjects with multiple AEs differing in relatedness will be counted once in the most related category. In addition, AEs categorized as "related" (i.e., those where the investigator assessment of relationship to study treatment is "possibly" or "related) will also be summarized by PT.

The incidence of AEs by severity will be summarized by SOC and PT using severity categories of mild, moderate, and severe. For a given SOC or PT, subjects with multiple AEs differing in severity will be counted once in the category of worst severity. The incidence of severe AEs will also be summarized by PT.

Deaths that occur will be described in detail in patient narratives. A listing of deaths will also be provided. While the number of deaths is expected to be small, tabulation will be performed if appropriate.

A summary of SAEs by SOC and PT will also be provided. Details of each SAE will also be listed, including subject ID, treatment group, system organ class/preferred term, date of onset, severity, and relationship to the study drug and action taken. In addition, a summary of treatment-related SAEs by SOC and PT will be provided.

The incidence of adverse events that led to study treatment discontinuation, study withdrawal, dose interruption, and dose reduction will each be presented by SOC and PT.

A listing of AEs leading to study treatment discontinuation and study withdrawal will also be presented. Adverse events that were treatment-emergent to the previous study yet led to study treatment discontinuation and study withdrawal in Study 109MS303 will be denoted by a negative onset day in the listing.

The incidence of adverse events of special interest will be summarized by SOC and PT. The adverse event of special interest categories may include the following:

- Flushing and other related symptoms;

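### The SAP plans crude AE proportions over unequal follow-up and no AE rate per subject-year; for continuing subjects, laboratory shifts skip parent-study dosing

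*SAP*

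**What the plan says.** **AE measure.** SAP 1.1 gives the primary objective as the long-term safety profile. SAP 6.5.3 defines AE incidence as a subject proportion, "defined as the proportion of subjects who had at least one occurrence of an event out of the number of subjects" in the relevant safety population. Events are in general counted to the end of each subject's follow-up.

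**Follow-up.** Under SAP 2.2, subjects who stopped treatment were treated as withdrawn, apart from lymphocyte follow-up. Others reached Week 384, and some went past it (SAP 3.4).

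**Denominator.** SAP 6.5.1 removes dosed subjects with no post-baseline safety follow-up, "in order not to inflate the denominator for calculation of incidences and percentages (and therefore deflate the incidences and percentages themselves".

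**Person-time.** SAP 6.3.6 says "the total number of subject-years of exposure to study medication will be presented", and time on medication is summarised for the Safety population. SAP 6.4.3 uses person-time for relapses: "The unadjusted ARR will be calculated for each treatment group as the total number of relapses divided by the total number of subject-years" of follow-up. Nothing in SAP 6.5 does the same for AEs.

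**Time intervals.** SAP 6.5.3: "The incidence of AEs by SOC and PT may also be presented by time intervals". These are proportions of the subjects followed in each interval.

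**Safety dataset.** The first dataset bullet of SAP 6.5.1 reads "Primary safety analyses will utilize the Study 109MS303 Safety Population with Combined Treatment Grouping and Study 109MS303 data only; and"; the second bullet keeps the same data restriction for the select analyses.

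**Laboratory baseline.** SAP 6.5.4 uses BG00012 Treatment Baseline. For subjects on BG00012 in the parent study, SAP 6.3.1 defines this as "the latest available value prior to or on the date of first exposure to study treatment in Study 109MS301 or 109MS302". SAP 6.5.5 uses the same baseline for vital signs.

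**The concern.** A subject followed for three months and one followed for eight years each add one unit to the denominator. For events that build up over time (malignancies, opportunistic infections, many serious events), the resulting percentage mixes risk with length of stay and has no stated time horizon. Readers will take it as the long-term risk, and it will be too low. The SAP accepts the principle when it drops subjects with no follow-up, but does not extend it to subjects with short follow-up.

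The laboratory point is separate. For a subject who took BG00012 throughout, the baseline precedes the parent study while the first eligible post-baseline value comes after entry to 109MS303. A worst value reached in between, and recovered from, does not appear in a shift table that seems to describe change since BG00012 began.

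**Working it through.** **1. What is divided by what**

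| Item | SAP section | Denominator | Status |
|---|---|---|---|
| AE incidence | 6.5.3 | subjects | planned |
| AE incidence by interval | 6.5.3 | subjects followed in the interval | optional |
| Exposure | 6.3.6 | none (total subject-years) | planned |
| Relapse rate | 6.4.3 | subject-years | planned |
| AE rate per subject-year | none | none | not planned |

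**2. Inputs for an illustration.** The plan gives no AE rate or attrition figure to reproduce.
- Randomised: 1738 (SAP 2.1).
- Ongoing: about 1000, a rounded count in the rationale of the protocol amendment that lengthened the study to 12 years. 1000/1738 = 0.575.
- Assumption: this retention applies t = 4 to 6 years after 109MS303 entry. The amendment's six-year figure appears to include parent-study time, so t = 4 may be nearer.
- Assumption: dropout is independent of AEs.
- Week 384: T = 384 × 7/365.25 = 7.36 years.
- Longest horizon: the Version 8 amendment rationale cites up to 12.5 years including the parent studies; 12.5 − 96 × 7/365.25 = 10.66 years.

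**3. Formulas** (constant AE hazard h, dropout hazard c)
- c = −ln(0.575)/t
- risk to T = 1 − exp(−hT)
- crude incidence = h/(h+c) × (1 − exp(−(h+c)T))
- mean time at risk = (1 − exp(−(h+c)T))/(h+c)

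**4. Results for h = 0.01, that is 1 per 100 subject-years.** Week-384 risk = 1 − exp(−0.0736) = 7.10%.

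| t (years) | c | Crude, stop at 7.36 y | Ratio to 7.10% | Mean years at risk | First events per 100 subject-years | Crude, all able to reach 10.66 y | Ratio to 7.10% |
|---|---|---|---|---|---|---|---|
| 4 | 0.138 | 4.48% | 0.63 | 4.48 | 1.0 | 5.36% | 0.755 |
| 5 | 0.111 | 4.88% | 0.69 | 4.88 | 1.0 | 6.00% | 0.846 |
| 6 | 0.092 | 5.17% | 0.73 | 5.17 | 1.0 | 6.50% | 0.915 |

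For h from 0.005 to 0.05, the ratio is 0.63 to 0.74 with follow-up stopped at Week 384 and 0.75 to 0.92 at 10.66 years. The second range is an upper bound, because it gives every subject the longest possible follow-up. Measured against the 10.66-year risk of 1 − exp(−0.1066) = 10.11%, the same crude values are only 5.36/10.11 = 0.53 to 6.50/10.11 = 0.64. The percentage therefore has no fixed horizon.

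At this one true rate, crude incidence to Week 384 falls on either side of the 5% cutoff that SAP 6.5.3 sets for frequently reported AEs.

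**5. Sensitivity, stopping at Week 384**
- 950 to 1050 remaining, constant hazard: 0.61 to 0.76.
- Events in year 1 only: 0.93 to 0.96. The same figures apply to a full 12-month interval, which falls about 4% to 7% short.
- Hazard rising linearly from zero, same cumulative hazard: 0.53 to 0.65. No document supports this shape; it shows direction only.

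**6. Laboratory window.** Parent-study dosing was 96 weeks (Protocol 5.2). For a subject dosed throughout to Week 384, the gap is 96/(96 + 384) = 20% of on-drug time. This is a maximum: some subjects switched therapy in the parent study (SAP 2.1) or had a gap before entry (SAP 2.2). SAP 6.5.4 names no dataset for the shift tables, so the pairing follows from reading 6.3.1, 6.5.1 and 6.5.4 together.

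**The case against.** **The rate can nearly be worked out from what is planned.** Subject-years will be shown for the Safety population. In the model above, subjects with an event divided by total subject-years gives 0.97 per 100 against a true 1.0 (for t = 4: 4.48% over (1 − exp(−cT))/c = 4.62 years). This is a fair point for rare events. It is still left to the reader, has no confidence interval, and mixes periods: AEs run to the end of follow-up, exposure to the last dose.

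**The analysis is descriptive and has other safeguards.** Serious events are listed with onset dates, narratives cover malignancies and potential opportunistic infections, and interval tables would remove most of the problem. This holds, but the interval tables are optional. Nothing in the SAP bars a rate; none is committed to.

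**Later follow-up narrows the gap.** It does, as step 4 shows, up to a bound that few subjects can have reached.

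**The laboratory choice is defensible.** A drug-free baseline is reasonable, and Protocol 16.4.2 focuses on extension data. SAP 6.2.2 and 6.2.3 together permit Combined Data for the Safety population. Lymphocyte analyses may use it (SAP 6.2.4), and absolute lymphocyte counts are summarised over the whole study (SAP 6.5.6). A listing also marks "Adverse events that were treatment-emergent to the previous study yet led to study treatment discontinuation and study withdrawal in Study 109MS303". All of this stands and limits the laboratory point to shift and change-from-baseline tables, plus vital signs.

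**Conclusion.** The point holds as an analysis that should be added; it does not invalidate the study. The SAP summarises AEs as crude proportions over unequal follow-up and commits to no person-time rate. For accruing events this understates long-term risk; for early events the effect is small. The ratios rest on inferred retention, constant hazards and dropout unrelated to AEs, so the actual size is unknown.

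Stronger readings that the documents do not support:
- *AE incidence is the primary endpoint.* The primary objective is the safety profile, and no single endpoint is named.
- *Risk is understated by about a third.* That figure depends on assumed attrition and on stopping at Week 384.
- *Comparisons between groups are biased.* Follow-up by group is not reported, so neither direction nor size can be stated.
- *The worst-value laboratory tables are mismatched.* The category counts in SAP 6.5.4 use no baseline.
- *The SAP departs from the protocol without recording it.* The protocol synopsis says combined long-term safety data *will* be summarised; Protocol 16.4.2 says *may*. This is an inconsistency within the protocol, and minor.

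**What to change.** 1. In SAP 6.5.3, keep crude incidence. Add first events per 100 subject-years at risk with 95% confidence intervals for serious AEs and AEs of special interest, overall and by 12-month interval. Count events and person-time over the same period.
2. Change the interval tables from *may* to *will*.
3. In SAP 6.5.4 and 6.5.5, label shift and change-from-baseline tables for continuing subjects as covering 109MS303 values only, or add a Combined Data shift table from BG00012 Treatment Baseline. If added, footnote the selection: entrants had to complete the parent study and could not have stopped BG00012 for an AE (Protocol 8.1 and 8.2). The table therefore does not estimate risk from BG00012 start in all treated subjects.
4. Reconcile the synopsis with Protocol 16.4.2 on combined safety data.

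The cost is SAP wording and extra tables from data already held. A single overall rate describes risk well only if the hazard is roughly constant, so it should always appear with the interval rates.
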